7.0 SUPPORTIVE CARE AND OTHER CONCOMITANT THERAPY

7.1 Concurrent Anticancer Therapy

Concurrent cancer therapy, including chemotherapy, radiation therapy, immunotherapy, or biologic therapy may NOT be administered to patients receiving study drug. If these treatments are administered the patient will be removed from protocol therapy.

7.2 Investigational Agents

No other investigational agents may be given while the patient is on study.

7.3 Supportive Care

Appropriate antibiotics, blood products, antiemetics, fluids, electrolytes and general supportive care are to be used as necessary. See [Section 7.5](#) for drugs that should not be used concomitantly due to potential interactions with MLN4924 (pevonedistat). For COG Supportive Care Guidelines see: <https://childrensoncologygroup.org/index.php/cog-supportive-care-guidelines> under Standard Sections for Protocols.

The use of GCSF is not required on this protocol, however filgrastim or biosimilar can be initiated per discretion of the treating physician in the setting of serious confirmed (culture proven) or suspicious infection. The use of filgrastim (G-CSF) or biosimilar is allowed at the treating physician's discretion to enhance neutrophil recovery when clinically indicated. If the treating physician determines that filgrastim use is indicated in Cycle 1, the pegylated formulation (pegfilgrastim) should not be used.

Pneumocystis Jirovecii pneumonia (PJP) prophylaxis: Patients should receive PJP prophylaxis with trimethoprim/sulfamethoxazole 5 mg/kg/day divided BID (max: 160 mg PO BID) for 2-3 consecutive days a week, or per institutional practice, until the end of protocol therapy.

Antifungal prophylaxis

Antifungal agents per institutional guidelines should be administered when ANC falls below 200/ μ L and continued until count recovery. See [Section 7.4.2](#) on CYP3A4 inducers and inhibitors for guidelines regarding concurrent administration with MLN4924 (pevonedistat).

Hospitalization/Hospital Environment

Hospitalization following each cycle of chemotherapy is strongly recommended until the absolute phagocyte count (sum of the neutrophils, bands and monocytes) rises for 2 successive days, and the patient is afebrile and clinically stable. An additional discharge criterion of an absolute neutrophil count (ANC) of at least 200/ μ L is also suggested.

It is recommended that patients should be assigned to rooms with special air filtration systems such as high efficiency particulate air filters (HEPA) or clean-air rooms with constant positive pressure airflow if at all possible.

Tumor Lysis Syndrome

Prophylaxis for tumor lysis syndrome (TLS) should be considered for patients at risk of developing rapid tumor lysis (e.g., patients with a high tumor burden or a higher number of circulating malignant cells). These patients should be followed closely and appropriate laboratory monitoring performed. Appropriate medical therapy should be provided for

patients who develop signs and symptoms consistent with rapid tumor lysis.

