THIS PROTOCOL IS FOR RESEARCH PURPOSES ONLY, SEE PAGE 1 FOR USAGE POLICY

of this interval must be discussed with the study chair and the study-assigned Research Coordinator prior to enrollment.

- c. Antibodies: ≥ 21 days must have elapsed from infusion of last dose of antibody, and toxicity related to prior antibody therapy must be recovered to Grade ≤ 1 .
- d. Hematopoietic growth factors: ≥ 14 days after the last dose of a long-acting growth factor (e.g. pegfilgrastim) or 7 days for short-acting growth factor. For agents that have known adverse events occurring beyond 7 days after administration, this period must be extended beyond the time during which adverse events are known to occur. The duration of this interval must be discussed with the study chair and the study-assigned Research Coordinator.
- e. Interleukins, Interferons and Cytokines (other than Hematopoietic Growth Factors): ≥ 21 days after the completion of interleukins, interferon or cytokines (other than Hematopoietic Growth Factors)
- f. Stem cell Infusions (with or without TBI):
 - Allogeneic (non-autologous) bone marrow or stem cell transplant, or any stem cell infusion including DLI or boost infusion: ≥ 84 days after infusion and no evidence of GVHD.
 - Autologous stem cell infusion including boost infusion: ≥ 42 days.
- g. Cellular Therapy: ≥ 30 days after the completion of any type of cellular therapy (e.g. modified T cells, NK cells, dendritic cells, etc.)
- h. XRT/External Beam Irradiation including Protons: ≥ 14 days after local XRT; ≥ 42 days after TBI, craniospinal XRT or if radiation to $\geq 50\%$ of the pelvis; ≥ 42 days if other substantial BM radiation.
- i. Radiopharmaceutical therapy (e.g., radiolabeled antibody, 131I-MIBG): ≥ 42 days after systemically administered radiopharmaceutical therapy.
- j. Patients must not have received prior exposure to MLN4924 (pevonedistat).

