12.2 Response Criteria for Patients with Leukemia

12.2.1 Complete Remission (CR)

Attainment of an M1 bone marrow (< 5% blasts and adequate marrow cellularity) with no evidence of circulating blasts or extramedullary disease and with recovery of peripheral blood counts (ANC \geq 1000/uL and platelet count \geq 100,000/uL). Flow cytometry may be useful to distinguish between leukemia and a regenerating bone marrow. There is no requirement for bone marrow cellularity.

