12.2.2 Complete Remission with Partial Recovery of Platelet Count (CRp)

Attainment of an M1 bone marrow (< 5% blasts) and no evidence of circulating blasts or extramedullary disease and with recovery of ANC \geq 1000/uL and platelet transfusion independence (defined as no platelet transfusions x 1 week).

12.2.3 Complete Remission with Incomplete Blood Count Recovery (CRi):

Attainment of an M1 bone marrow (<5% blasts) and no evidence of circulating blasts or extramedullary disease and with ANC $<$ 1000/uL or platelet count $<$ 100,000/uL without platelet transfusion independence (defined as no platelet transfusions x 1 week).

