12.2.4 Partial Response

Attainment of M2 marrow status (\geq 5% or $<$ 25% blasts cells and adequate cellularity) and at least 50% decrease in bone marrow blast percent from baseline. Bone marrow must have adequate cellularity (e.g. \geq 10% if a biopsy is performed) to determine response. PR status will not be included in the calculation of response to the regimen. A repeat bone marrow aspiration within 14 days may be required to distinguish between a PR and increased blasts caused by bone marrow regeneration, and is left to the discretion of the investigator.

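### CR can be met on a recently transfused platelet count while the lesser CRp cannot, so a platelet transfusion can move a patient from CRi to CR

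*Combined protocol and SAP*

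**What the plan says.** Supportive care is open. Section 7.3 states: "Appropriate antibiotics, blood products, antiemetics, fluids, electrolytes and general supportive care are to be used as necessary". It also allows filgrastim at the treating physician's "discretion to enhance neutrophil recovery when clinically indicated". The only formulation limit is that, in Cycle 1, "the pegylated formulation (pegfilgrastim) should not be used".

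Section 12.2 grades remission. All three categories need an M1 marrow (under 5% blasts) and no circulating blasts or extramedullary disease. They differ in the count conditions:

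- CR (12.2.1): "with recovery of peripheral blood counts", given as ANC of at least 1000/uL and platelets of at least 100,000/uL. Transfusion is not mentioned.
- CRp (12.2.2): the same ANC threshold plus "platelet transfusion independence (defined as no platelet transfusions x 1 week").
- CRi (12.2.3): ANC below 1000/uL, or platelets below 100,000/uL "without platelet transfusion independence (defined as no platelet transfusions x 1 week").

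Section 12.2.4 adds: "PR status will not be included in the calculation of response to the regimen". It excludes nothing else, so CR, CRp and CRi all appear to count as response.

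**The concern.** The categories are meant to be ordered, with CR requiring the fullest count recovery. For platelets the order breaks. The middle category asks whether the patient has been free of platelet transfusion for a week, and the top category does not. A patient can fail the transfusion test for CRp and still be CR, because the transfusion itself may have carried the count past 100,000/uL.

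At stake is the reported CR rate, and with it the split of remissions between CR and CRi. Section 1.2 makes antitumor activity the secondary aim, and Section 2.5 says that results will lead to a phase 2 trial. If transfused counts qualify, the CR rate partly reflects transfusion practice rather than marrow recovery.

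**Working it through.** The plan states no figure on this point, so there is none to reproduce. The check applies the count rules of Sections 12.2.1 to 12.2.3 to a patient who already meets the marrow, blast and extramedullary conditions. Transfused means a platelet transfusion within the past week. The ANC and platelet values are illustrative, chosen on either side of the stated thresholds.

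| ANC (/uL) | Platelets (/uL) | Transfused | Category as written |
|---|---|---|---|
| 1200 | 110,000 | no | CR (also meets CRp) |
| 1200 | 110,000 | yes | CR (fails CRp) |
| 1200 | 90,000 | no | CRp |
| 1200 | 90,000 | yes | CRi |
| 800 | either | yes | CRi |
| 800 | either | no | CRi, if the transfusion clause in 12.2.3 qualifies platelets only |

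The second and fourth rows show the inversion. With the same ANC and the same recent transfusion, the patient is CRi at 90,000/uL and CR at 110,000/uL. Both results hold whichever way the transfusion clause in 12.2.3 is read.

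**Size.** If k patients move from CRi to CR among n assessed, the CR rate rises by k/n and the CRi rate falls by k/n. The pooled rate changes by k/n − k/n = 0. For k = 1:

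- n = 6: 1/6 = 16.7 points
- n = 12: 1/12 = 8.3 points
- n = 18: 1/18 = 5.6 points
- n = 23: 1/23 = 4.3 points

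The documents name no response denominator. Eighteen is the maximum number evaluable for dose confirmation in Section 11.1 and is used here as an assumption. They also do not say how often a count of 100,000/uL or more would follow a recent transfusion.

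**Plausibility.** Section 5.3 places the Cycle 1 disease assessment on Days 36-39. Section 2.1 cites, from an earlier trial of an intensive regimen that it regards as comparable, a median of 38 days to platelets above 50,000/uL. That is half the CR threshold, so many patients may still be recovering when first classified. It does not show how many would have transfused counts at or above 100,000/uL.

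**What does not move.** Section 5.3 lets CR, CRp and CRi proceed to Cycle 2 alike. The dose decision in Section 11.3 rests on DLT counts and does not use response categories.

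**The case against.** The strongest defence is that recovery in Section 12.2.1 already means unsupported recovery. Sections 2.1 and 6.1.1 qualify the platelet count by transfusion when they describe hematologic recovery, so the intent may be the same. That is a fair reading of intent, but Section 12.2.1 does not state it. The neighbouring categories do state a transfusion condition, so a literal classifier would treat its absence from CR as deliberate.

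A second defence is that nothing depends on the split. This largely stands. Section 11.5 calls the response analyses descriptive and hypothesis-generating, and Section 2.1 foresees a phase 2 trial with its own azacitidine plus fludarabine/cytarabine comparator.

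Three stronger readings are tempting, and the documents do not support them.

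- A reader might infer that filgrastim causes the same inversion. It can lift a patient out of CRi: raising ANC from 800 to 1200/uL gives CR at platelets of 110,000/uL, or CRp at 60,000/uL if transfusion-independent. But CR and CRp use the same ANC threshold and neither asks about growth factor, so no ordering is broken.
- A reader might borrow the entry intervals in Section 4.1.4.1 d (14 days after a long-acting agent, "or 7 days for short-acting growth factor") as a washout for the response ANC. Those intervals govern prior therapy before enrollment, and the entry marrow criterion in Section 4.1.5.6 sets only a hemoglobin level, so no ANC is judged there. A later count could also fall outside follow-up: the last pevonedistat dose is on Day 5, and Section 10.2 ends study participation 30 days later, on about Day 35.
- A reader might set the shift beside the 59% versus 69% CR difference in Section 2.1. That comparison comes from a trial that randomized 394 patients, with filgrastim in both arms and a response definition not given here. It does not calibrate this effect.

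Nor do the documents show that supported counts would change any DLT call.

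**Conclusion.** The platelet inversion is real on the text, and no other section corrects it. As written, a transfusion can turn CRi into CR and overstate the CR rate relative to a definition consistent with CRp. Each such patient adds 5.6 points if n = 18, or 4.3 to 16.7 points for n from 23 down to 6. The number affected is unknown and could be zero.

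The effect is confined to how remissions divide between CR and CRi in a descriptive secondary aim. This is a minor drafting correction, worth making before response is reported. It is no evidence that overall response is overstated.

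**What to change.** Leave supportive care as it is and make two linked edits to the definitions.

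1. In Section 12.2.1, add the platelet transfusion independence condition already defined in Section 12.2.2.
2. In Section 12.2.3, state that a patient with an M1 marrow who meets both count thresholds but is not platelet-transfusion independent is CRi.

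The second edit is essential. With the first alone, the patient with ANC 1200/uL, platelets 110,000/uL and a recent transfusion would fail CR and CRp, and would also fail CRi because neither count is low. That patient would leave the pooled remission rate. A simple wording that closes the gap is to make CRi apply when ANC is below 1000/uL, or when the patient is not platelet-transfusion independent at any platelet count. The three categories then cover every row of the table, with CR taking precedence over CRp.

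The cost is small. The condition looks back over the preceding week, and applying Section 12.2.2 already requires platelet transfusion dates. The sponsor should confirm that the separate case report forms capture them. The downside is that the reported CR rate may be slightly lower.

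No growth-factor washout for ANC and no change to DLT review is needed. At most, report descriptively whether filgrastim was in use at response assessment.

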7.4 Concomitant Medications

7.4.1 Corticosteroid Therapy

Corticosteroids should not be used as anti-emetic therapy. Corticosteroid therapy is not permissible except for the following indications:

- As treatment or prophylaxis for anaphylactic reactions
- As a treatment for symptoms of ARA-C syndrome including fever, rash, or conjunctivitis (see [Section 6.3.2](#))
- Suspected or confirmed adrenal insufficiency

7.4.2 CYP3A4 Inducers and Inhibitors

In vitro, MLN4924 (pevoneditat) is metabolized predominantly by CYP3A4 with a small contribution from CYP2D6. Based on drug-drug interaction study results, administration of MLN4924 (pevoneditat) with moderate and strong CYP3A inhibitors and P-gp inhibitors is permitted, while use of strong CYP3A inducers should be avoided. Strong inducers of CYP3A4 should be discontinued within 14 days prior to the first dose of MLN4924 (pevoneditat) and are prohibited for the duration of the study (see [Appendix IX](#)).

7.4.3 Concomitant administration of BCRP inhibitors (e.g., cyclosporine, eltrombopag) should be avoided, however, limited use is permitted if clinically necessary and no suitable alternative exists. In this case, a patient may receive the BCRP inhibitor from 24 hours after the last MLN4924 (pevoneditat) dose until 72 hours before the next MLN4924 (pevoneditat) dose.

7.4.4 Acetaminophen and acetaminophen-containing products may be used judiciously but should not exceed a dose of 37 mg/kg/day (maximum 2 g in 24 hours) on days MLN4924 (pevoneditat) is administered.

8.0 EVALUATIONS/MATERIAL AND DATA TO BE ACCESSIONED

8.1 Required Clinical, Laboratory and Disease Evaluation

All clinical and laboratory studies to determine eligibility must be performed within 7 days prior to enrollment unless otherwise indicated. Laboratory values used to assess eligibility (see [Section 4.0](#)) must be no older than seven (7) days at the start of therapy. Laboratory tests need **not** be repeated if therapy starts **within** seven (7) days of obtaining labs to assess eligibility. If a post-enrollment lab value is outside the limits of eligibility, or laboratory values are older than 7 days, then the following laboratory evaluations must be re-checked within 48 hours prior to initiating therapy: CBC with differential, bilirubin, ALT (SGPT) and serum creatinine. If the recheck is outside the limits of eligibility, the patient may not receive protocol therapy and will be considered off protocol therapy. Bone marrow aspirate and/or biopsy, must be obtained within 14 days prior to start of protocol therapy. See [Appendix VIII](#) for Therapy Delivery Maps for each cycle.

STUDIES TO BE OBTAINED	Pre-Study	During Cycle 1	During Cycle 2
History	X	Weekly	X [^]
Physical Exam with vital signs ⁷	X	Weekly	X [^]
Height, weight, BSA	X	Weekly	X [^]
Performance Status	X		
CBC, differential, platelets	X	Twice Weekly	X [^]
Pharmacokinetics ¹	X	X	
Electrolytes including Ca ⁺⁺ , PO ₄ , Mg ⁺⁺	X	Weekly ⁶	X [^]
Creatinine	X	Weekly	X [^]
ALT, AST, bilirubin (fractionated) ⁸	X	Prior to each dose of MLN4924 (pevoneditat), then weekly	Prior to each dose of MLN4924 (pevoneditat), then weekly
Albumin	X		X [^]
Pregnancy Test ²	X		X [^]
ECHO or gated radionuclide study	X	X ⁵	X ⁵
EKG	X	X ⁵	X ⁵
Bone Marrow Aspirate and/or biopsy	X	End of Cycle 1	End of Cycle 2
CSF for cell count, cytospin	X	End of Cycle 1	End of Cycle 2
PD (mRNA Transcript Levels) ³		X	
PD (NEDDylated Protein Analysis) ⁴		X	

[^] Studies may be obtained within 72 hours prior to the start of the subsequent cycle.

¹ See [Section 8.2](#) for timing of PK studies.

² Women of childbearing potential require a negative pregnancy test prior to starting Cycle 1 treatment and prior to Cycle 2; sexually active patients must use an acceptable method of birth control. Abstinence is an acceptable method of birth control.

³ See [Section 8.3](#) for timing of optional PD – mRNA Transcript Level studies.

⁴ See [Section 8.4](#) for timing of optional PD – NEDDylated Protein Analysis studies.

⁵ Echo and EKG performed prior to Cycle 2 therapy (echo and EKG done at the end of Cycle 1 can count as long as it is done within 2 weeks prior to the start of Cycle 2 and before any subsequent therapy). An additional echo and EKG are to be obtained at the end of Cycle 2.

⁶ Monitor as clinically indicated for tumor lysis.

⁷ Vital signs should be checked prior to each MLN4924 (pevoneditat) infusion as well as at the end of treatment.

⁸ ALT, AST, and bilirubin tests must be performed and read prior to each dose of MLN4924 (pevoneditat).

8.2 Pharmacology (Required)

8.2.1 Description of Studies and Assay

Pharmacokinetics (PK) will be performed to determine the PK of MLN4924 (pevoneditat) in children. Serum will be collected and MLN4924 (pevoneditat) concentration will be determined by a validated liquid chromatography/tandem mass spectrometry (LC/MS/MS) assay. Samples will be analyzed by Covance Madison BioA.

8.2.2 Sampling Schedule (See [Appendix IV-A](#) and [Appendix IV-B](#))

8.2.2.1 For patients ≤ 10 kg, blood samples will be obtained at the following time points during Cycle 1:

THIS PROTOCOL IS FOR RESEARCH PURPOSES ONLY, SEE PAGE 1 FOR USAGE POLICY

- Day 1: pre-dose, at the end of infusion, and at 4 – 6, and 24 hours after the end of infusion
- Day 5: pre-dose, at the end of infusion, and at 4 – 6, and 24 hours after the end of infusion

8.2.2.2 For patients > 10 kg, blood samples will be obtained at the following time points during Cycle 1:

- Day 1: pre-dose, at the end of infusion, and at 1, 2, 4, 6 – 8, and 24 hours after the end of infusion
- Day 3: pre-dose
- Day 5: pre-dose, at the end of infusion, and at 1, 2, 4, 6 – 8, 24, and 48 **OR** 72 hours after the end of infusion

8.2.3 Sample Collection and Handling Instructions

Blood samples (3 mL) will be collected into a chilled Becton-Dickinson Vacutainer K2 EDTA tube at a site distant from the infusion for pharmacokinetic evaluation. Samples cannot be drawn from the 2nd lumen of a multi-lumen catheter through which drug is being administered. Record the exact time that the sample is drawn along with the exact time that the drug infusion begins and ends.

8.2.4 Sample Processing

- Collect 3.0 mL of venous blood into a chilled K2EDTA lavender top Becton-Dickinson Vacutainer.
- Gently invert the Vacutainer 8 to 10 times to mix the additive with the collected blood prior to centrifugation and place immediately on ice.
- Centrifuge the Vacutainers for 10 minutes at approximately 1100 to 1300 x g (RCF) at approximately 4°C in a refrigerated centrifuge. Note: if using a collection device other than Becton-Dickinson, refer to manufacturer's instruction for proper centrifugation force and time.
- Immediately following centrifugation, gently remove plasma from the packed cells and transfer into 2 appropriately labeled 2.0 mL cryogenic vials. To ensure a more homogeneous sample, transfer all plasma into one cryovial. From there, split the plasma evenly between the 2 aliquots. A minimum of 0.6 mL needs to be obtained for each aliquot.
- Cap the labeled storage tubes and freeze the plasma samples immediately at approximately -70°C or lower. If a -70°C freezer is not available, freeze and store samples at -20°C. No more than 45 minutes will elapse between blood collection and freezing the plasma sample.
- Store samples frozen at approximately -70°C or lower until shipment.

Note: If a -70°C freezer is not available, the samples may be stored at approximately -20°C in a commercial grade freezer with no auto-defrost until shipment.

8.2.5 Sample Labeling

Each tube must be labeled with the patient's study registration number, the study I.D., and the date and time the sample was drawn. Data should be recorded on the Pharmacokinetic Study Form ([Appendix IV-A](#); [Appendix IV-B](#)), which must accompany the sample(s).

THIS PROTOCOL IS FOR RESEARCH PURPOSES ONLY, SEE PAGE 1 FOR USAGE POLICY

8.2.6 Sample Shipping Instructions
See [Appendix XIII](#).8.3 **Pharmacodynamics - mRNA Transcript Levels (Optional)**8.3.1 Description of Studies and Assay

Peripheral blood will be collected from consenting patients to evaluate the effects of MLN4924 (pevoneditat) on mRNA transcript levels of genes that have been shown to be induced by MLN4924 (pevoneditat) mediated NAE inhibition. Samples will be analyzed by reverse transcription-polymerase chain reaction (RT-PCR) by Takeda Pharmaceuticals.

8.3.2 Sampling Schedule (See [Appendix V](#))

Blood samples will be collected from consenting patients at the following time points during Cycle 1:

- Day 1: pre-dose
- Day 3 **OR** Day 5: 3 hours and 6 hours after the end of MLN4924 (pevoneditat) infusion (which is given after azacitidine)

8.3.3 Sample Collection and Handling Instructions

Blood samples (2 ml) will be collected in citrate vacutainer tubes at a site distant from the infusion in consenting patients. Record the exact time that the sample is drawn along with the exact time that the drug infusion begins and ends.

